4 CLINICAL INVESTIGATION DESIGN

4.1 CLINICAL INVESTIGATION DESIGN

The INTELLECT 2-HF Study is a prospective, non-randomized multicenter, single-arm observational study, which will be conducted at up to 25 U.S. centers, and will enroll up to 100 subjects.

The expected duration of enrollment is approximately 18 months with a six month follow-up period. Patients will exit the study when they complete their six month follow-up visit. The total duration of the clinical investigation is expected to be approximately two years.

Patients will be managed with the goal of achieving a PA diastolic pressure in a target range between 8 and 15 mmHg. Clinician discretion is allowed on how to reach this target range by remotely adjusting diuretic/ vasodilator therapy, or by changing pump speeds at clinic visits. The change implemented, and reason for the change, must be documented in the CRF. If no change is made when the patient is outside the target range, the clinician must document the clinical rationale for not making a change. It is recommended that adjustments to diuretic medications be the first approach unless an alternate approach is clinically more appropriate. Pump speed changes in these patients are expected to be infrequent.

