4.4.1 Inclusion Criteria

To participate in this clinical investigation, the subject must meet all of the following inclusion criteria:

1. Subject has CardioMEMS HF PA Sensor and a commercially-approved HeartMate LVAD (Group A)

OR

This confidential document is the property of Abbott and shall not be reproduced, distributed, disclosed or used without the express written consent of Abbott.

Subject has commercially-approved HeartMate LVAD is experiencing NYHA class III symptoms, and has had a previous HF hospitalization and meets FDA indications for CardioMEMS. The CardioMEMS sensor must be implanted within 72 hours of consent (Group B)

2. Signed an informed consent form and agreed to provide access to patient and device data (including CardioMEMS Merlin.net data)
3. No connectivity or transmission problems with CardioMEMS
4. On HeartMate LVAD support for at least 3 months
5. Age \geq 18 years

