5.2 INFORMED CONSENT PROCESS

The Principal Investigator or his/her authorized designee will conduct the Informed Consent Process, as required by applicable regulations and the center's IRB. Patients from Group A will provide consent for the sponsor to access CardioMEMS historical data collected prior to study enrollment as well as current data from the Merlin.net website. Group B will provide consent to review all data collected in the study. The CardioMEMS sensor must be implanted within 72 hours of consent.

This informed consent process will include a verbal discussion with the subject on all aspects of the clinical investigation that are relevant to the subject's decision to participate, such as details of clinical investigation procedures, anticipated benefits, and potential risks of clinical investigation

This confidential document is the property of Abbott and shall not be reproduced, distributed, disclosed or used without the express written consent of Abbott.

participation. During the discussion, the Principal Investigator or his/her authorized designee will avoid any improper influence on the subject and will respect the subject's legal rights. The subject shall be provided with the informed consent form written in a language that is understandable to the subject and has been approved by the center's IRB. The subject shall have adequate time to review, ask questions and consider participation.

If the subject agrees to participate, the Informed Consent form must be signed and dated by the subject and by the person obtaining the consent. The signed original will be filed in the subject's hospital or research charts, and a copy will be provided to the subject.

Failure to obtain informed consent from a subject prior to clinical investigation enrollment should be reported to Sponsor within 5 working days and to the reviewing center's IRB according to the IRB's reporting requirements.

During the clinical investigation, when new information becomes available that can significantly affect a subject's future health and medical care, the Principal Investigator or his/her authorized designee, will provide this information to the subject. If relevant, the subject will be asked to confirm their continuing informed consent in writing.

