5.5.1 Baseline

The following baseline assessments and information will be collected after informed consent is obtained at the baseline visit. For Group A patients, these assessments will be done after consent. For Group B patients, assessments will be performed after consent and within 3 days prior to the CardioMEMS™ HF System implant.

- Medical history, physical and documentation of Inclusion/ exclusion information,
- Heart failure visit assessment including assessing and recording NYHA class, height, weight and vital signs
- Documentation of demographic information
- Documentation of HeartMate device model and CardioMEMS™ study device sensor serial number information (for group B this CRF will be completed after successful CardioMEMS implant)
- Current Medications: anticoagulation/anti platelet, and cardiovascular medications including ACE inhibitors, ARBs, beta blockers, nitrates, hydralazine, aldosterone antagonists, digoxin and diuretics. Other medications do not need to be tracked.
- Documentation of current pump parameters
- Administer Six Minute Hall Walk test (6MHWT). For Group A, CardioMEMS PA reading taken before 6MHW test (at rest) and immediately following 6MHW test (see Appendix D), ideally within one minute of test
- Administer EQ-5D-5L survey

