6 DATA ANALYSIS CONSIDERATIONS

This is a feasibility study evaluating commercially approved devices and has only descriptive endpoints. These endpoints will be evaluated via descriptive summary statistics without formal tests of hypothesis. The goal of this study is to gather data from subjects with both the CardioMEMS™ HF System and an FDA-approved HeartMate II™ (and HeartMate 3™ upon FDA approval) Left Ventricular Assist Device (LVAD). Both devices are commercially approved and will be used, as indicated, per the labeling. The underlying belief is that maintaining pulmonary artery pressure within a target range using CardioMEMS hemodynamic monitoring will improve outcomes in HeartMate LVAD patients.

Statistical analyses will be conducted to understand the role of hemodynamic monitoring in LVAD patients in order to:

- Characterize PA pressure measurements with the CardioMEMS HF System in LVAD patients under different clinical and physiologic conditions

To characterize PA pressure in LVAD patients, descriptive statistics will be used to quantify pressure at baseline, throughout the study and at 6 months using available data throughout the study. Raw PA pressures will be analyzed similarly at 1, 3, and 6 months. To characterize the impact of physical activity on PA pressure, descriptive statistics will be used to quantify the change in PA pressure before and after the 6MHW test.

- Characterize the effects of PA pressure on functional status, quality of life, and hospital readmissions of LVAD patients

To characterize the effects of PA pressure on clinical outcomes, patients will also be divided into subgroups based on time spent in the target PA pressure range and overall change in PA pressure during the follow-up period. Hospital readmissions and changes in functional status and quality of life will be quantified in these subgroups. The results can be used to find potential pressure ranges that are achievable in LVAD patients and have good clinical outcomes.

- Evaluate target ranges for PA pressure and assess the impact of medication and pump speed changes on PA pressures

The percentage of days that PA pressure is in the target range at different points in the study will be used to assess the impact of medication and pump speed changes on PA pressures.

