The results of this study will be used to design future clinical trials. Any statistical significance levels (p-values) obtained from the statistical tests will be used to help identify endpoints that are sensitive to the potential benefits achieved from utilizing the CardioMEMS HF System to monitor and treat LVAD patients. Note that Group A and B patients will be analyzed together as one group and also as separate groups.

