6.5 INTERIM ANALYSIS

Interim analyses will be conducted as data accumulates in this study. As there are no hypotheses to be tested, type I error control is not applicable.

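### Section 6 would use p-values from unnamed tests to help pick endpoints sensitive to CardioMEMS benefit; this conflicts with the plan's no-testing statements, and for clinical endpoints in a single arm a p-value cannot show that sensitivity

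*Combined protocol and SAP*

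**What the plan says.** Section 6 opens by describing a feasibility study with descriptive endpoints: "These endpoints will be evaluated via descriptive summary statistics without formal tests of hypothesis". Section 6.5 goes further: "As there are no hypotheses to be tested, type I error control is not applicable". Section 6.1.1 agrees with both. It lists counts, means, standard deviations, medians, ranges, percentages and events per patient-time, and names no test or threshold.

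The last paragraph before Section 6.1 then says: "Any statistical significance levels (p-values) obtained from the statistical tests will be used to help identify endpoints that are sensitive to the potential benefits" of using CardioMEMS to monitor and treat LVAD patients. It also says that the results will serve to design future trials, and that Groups A and B will be analyzed both together and apart.

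Four features of the design bear on what such a p-value could mean.

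- Section 4.1 describes a "prospective, non-randomized multicenter, single-arm observational study".
- Group A has the sensor before entry. Section 5.2: "Patients from Group A will provide consent for the sponsor to access CardioMEMS historical data collected prior to study enrollment".
- A Group B patient, under Section 4.4.1, "is experiencing NYHA class III symptoms, and has had a previous HF hospitalization". Section 5.5.1 says that Group B's baseline "assessments will be performed after consent and within 3 days prior to the" sensor implant, and NYHA class is among those assessments.
- To relate pressure to outcome, Section 6 says that patients will be "divided into subgroups based on time spent in the target PA pressure range and overall change in PA pressure during the follow-up period".

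**The concern.** Two things look wrong. First, a p-value needs a null hypothesis, and Section 6.5 says there is none; it waives type I error control on that ground. The plan gives p-values a task all the same.

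Second, the design cannot support that task for the clinical endpoints. To say that an endpoint is sensitive to the benefit of monitoring, one needs a contrast between monitoring and its absence. This study offers change over time in a single arm and comparisons of patients sorted by their own follow-up pressure.

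What is at stake is the next trial. Its design is a stated use of these results, and this sentence is the only guidance the plan gives on choosing endpoints from them. An endpoint such as NYHA class could be carried forward because of how Group B was selected, not because it responds to monitoring.

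**Working it through.** The plan states no figure on this point that could be reproduced. Its only design figure, 100 subjects (Section 6.2), comes without inputs and is not in dispute.

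**Step 1. Go through the comparisons that the plan offers.**

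- *Change from baseline, Group A.* The sensor is in place at baseline, so the change does not contrast monitoring with no monitoring. It also carries any time effect.
- *Change from baseline, Group B.* NYHA class is both an entry condition and an endpoint (Section 6.1.1, item 6), and the baseline value is taken at about the time of selection. Some regression to the mean is plausible, on top of any time effect.
- *Hospitalization rates* (items 8 and 9). These are summarized over the 6 months only, with no baseline comparator.
- *PA-pressure subgroups* (item 10). They are formed on follow-up pressure, so a difference may reflect prognosis.

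In each case a small p-value shows change or association at most. Naming the tests or adjusting for multiplicity would not alter that.

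**Step 2. Illustrate the size for NYHA in Group B with no true change.**

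From the documents: about 20% of LVAD patients are in class III or IV (Section 2); NYHA has five classes, I, II, IIIA, IIIB and IV (Appendix C). Assumed, because the documents are silent: 30 Group B patients; class IV share 1-5%; IIIB 30-70% of class III; an exact two-sided 0.05 sign test of improved against worsened, ties dropped; a latent standard normal severity X at baseline and Y at follow-up, same mean and variance, correlation r.

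Cut points for the middle case (class IV 2%, IIIB half of class III, so class III share 0.20 - 0.02 = 0.18):

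- a = Φ⁻¹(1 - 0.20) = 0.842 (II to IIIA)
- b = Φ⁻¹(1 - 0.02 - 0.5 × 0.18) = Φ⁻¹(0.89) = 1.227 (IIIA to IIIB)
- c = Φ⁻¹(1 - 0.02) = 2.054 (IIIB to IV)

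Then

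- p(improve) = [P(a < X < b, Y < a) + P(b < X < c, Y < b)] / 0.18
- p(worsen) = [P(a < X < b, Y > b) + P(b < X < c, Y > c)] / 0.18

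The number of patients who change class is M ~ Bin(n, p(improve) + p(worsen)). Given M = m, the number improved is K ~ Bin(m, p(improve)/[p(improve) + p(worsen)]). Improvement is declared when K = k satisfies 2·P(Bin(m, 0.5) ≥ k) ≤ 0.05 with k > m/2. With p(improve) = p(worsen) this happens in at most 2.5% of studies.

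| r | improve | worsen | declared, n = 30, middle case | declared, n = 30, full range |
|---|---|---|---|---|
| 0.98 | 20% | 10% | 9.5% | 7-11% |
| 0.95 | 31% | 14% | 18.3% | 14-23% |
| 0.90 | 40% | 17% | 31.7% | 22-39% |

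The improve and worsen columns help in judging r: at 0.98 about 30% of patients change class by chance alone, at 0.90 more than half.

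**Step 3. Vary what is unknown.** For r = 0.98, 0.95 and 0.90 in turn, over the same ranges:

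- n = 10: 0-1%, 2-3%, 5-6%
- n = 20: 4-5%, 8-12%, 14-23%
- n = 50: 13-24%, 22-43%, 38-64%

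Appendix C also scores inotrope-dependent patients as class IV at post-enrollment visits only, which pushes towards worsening. If a share q is moved this way, p(improve) becomes (1 - q)·p(improve) and p(worsen) becomes (1 - q)·p(worsen) + q. In the middle case at n = 30, q = 5% (assumed) gives about 3%, 8% and 17%; q = 10% gives about 1%, 3% and 8%.

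**The case against.** The sentence is soft. It speaks of any p-values that may arise, says they will help identify endpoints, and sets no threshold; the opening of Section 6 excludes only formal tests. The study is a feasibility study with no success criteria (Section 6.4) and no statistical stopping criteria (Section 6.6). All of this stands, and it limits the consequence. It does not remove the conflict with Section 6.5, which denies any hypothesis, formal or not.

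A reader might infer that the plan has a selection rule, or that it treats a small p-value as proof of benefit. The documents support neither. A reader might also infer that no comparison in the study could carry information. That goes too far as well: patients are managed to a protocol pressure range after enrollment (Section 5.6), and Group A's earlier readings could give a pre-period for the PA-pressure endpoint. They give no comparator for walk distance, NYHA class, quality of life or hospitalization.

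The regression argument concerns one endpoint in one group of unknown size. The model draws Group B from all LVAD patients; if class III symptoms are persistent, as Section 2 suggests, the effect is smaller, and the inotrope scoring in Appendix C may offset it. These limits stand. The argument in Step 1 does not rest on the model.

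Finally, intervals in place of p-values leave attribution as weak as before. That is so, and the caveat sentences in the fix are there for that reason.

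**Conclusion.** The point holds. The sentence contradicts the opening of Section 6 and Section 6.5, and gives p-values a use that this design does not support for the clinical endpoints. The size cannot be had from the documents, which give no test, no Group A/B split and no NYHA repeatability. The illustration runs from near or below nominal (very few Group B patients with high r, or appreciable inotrope scoring) to well above it (30 or more patients at r = 0.95 or below, without that scoring). It should be read as a range, not an estimate.

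The consequence is modest: no conclusion or stopping decision of this study depends on the sentence. It should still be changed, because it would misdirect the use that Section 6 itself names for the results, the design of later trials.

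**What to change.** Delete the p-value sentence in Section 6; Sections 6, 6.1.1 and 6.5 then agree. Add 95% confidence intervals to the planned change-from-baseline summaries for Group A, Group B and pooled. With 100 patients the half-width for a mean change is about 1.96/√100 = 0.196 SD of the change; with 30 it is 1.96/√30 = 0.358 SD. Use the estimates, their variability and data completeness as planning inputs, and say that endpoints will not be chosen by whether an interval excludes zero.

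Add two statements: that change from baseline includes regression to the mean and time effects and is not an estimate of CardioMEMS benefit; and that the PA-pressure subgroups, being formed on follow-up pressure, show association only.

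Optional: a baseline-to-visit NYHA shift table, and a confidence interval for hospitalization rates that allows for repeat events in one patient, for example a bootstrap over patients.

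The cost is one sentence removed, a few added and some table columns, with no new data. The sponsor gives up calling an endpoint significant on the strength of this study.

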6.1 ANALYSIS OF ENDPOINTS

6.1.1 Descriptive Endpoints

The following endpoints will be analyzed using descriptive statistics. Continuous variables will be summarized using numbers of subjects, mean, standard deviation, median, minimum, and maximum. Categorical variables will be summarized using frequency and percentages. Rate data will be summarized using events per patient-time.

1. Change in Six Minute Hall Walk (6MHW) distance will be summarized as change from baseline and using raw values, at 1, 3, and 6 months.
2. Changes in CardioMEMS™ PA pressure over time will include PA systolic, diastolic and mean pressures; heart rate; and cardiac output (calculated using latest algorithm for CardioMEMS) and will be summarized at baseline, throughout the study, and at 6 months.
3. Percentage of days over 6 months that PA diastolic pressure is between 8 and 15 mmHg will be summarized using the total number of days that pressures were measured as the denominator. The percentage will also be calculated at different points during the study. This endpoint will be used to assess the impact of medication and pump speed changes on PA pressures.
4. Changes in PA pressure before the 6MHW test to after the 6MHW test will be summarized at baseline (Group A only) and at 1, 3, and 6 months for both groups.
5. Device malfunction will include all instances of loss of performance of either device and will be summarized separately by device and type of loss of performance at 1, 3, and 6 months.
6. NYHA classification will be analyzed as a categorical variable and as a continuous variable at baseline, 1, 3, and 6 months. Change from baseline in NYHA will be analyzed similarly.
7. Health related quality of life (EQ-5D-5L) total score and visual analogue scale will be scored using the recommended scoring algorithms and analyzed at baseline, 1, 3, and 6 months. The change from baseline in EQ5D-5L will be analyzed similarly.
8. All-cause hospitalization rate will be summarized over 6 months in units of events per patient-time.
9. Heart failure hospitalization rate including emergency department visits, or unscheduled clinic visits for worsening HF, volume management, and/or cardiovascular medication management will be summarized over 6 months in units of events per patient-time.
10. Change in 6MHWD, NYHA class, EQ-5D-5L, or unscheduled hospitalizations will be analyzed descriptively according to subgroups based on PA diastolic pressure.

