4.2 OBJECTIVES

INTELLECT 2 will gather data from patients with both the CardioMEMS™ HF System and HeartMate™ LVAD. Both devices are commercially approved and will be used, as indicated, per the labeling. The objective of this clinical investigation is to understand the role of hemodynamic monitoring in LVAD patients and:

This confidential document is the property of Abbott and shall not be reproduced, distributed, disclosed or used without the express written consent of Abbott.

- Characterize PA pressure measurements with the CardioMEMS HF System in LVAD patients under different clinical and physiologic conditions
- Characterize the effects of PA pressure on functional status, quality of life, and hospital readmissions of LVAD patients
- Evaluate target ranges for PA pressure and assess the impact of medication and pump speed changes on PA pressures

The results from this study will facilitate the design of future studies in this patient population, leading to the development of clinical strategies for managing LVAD patients using information from an implantable hemodynamic monitor.

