5.9 RAMP STUDIES

When any ramp studies are performed per institutional protocol, PA pressure data will also be collected with the CardioMEMS™ system with each change in pump speed.

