6.1.2 Additional Descriptive Data Analyses

1. CardioMEMS™ PA pressure data during LVAD speed ramp test, when done as standard of care, will be summarized over 6 months.

This confidential document is the property of Abbott and shall not be reproduced, distributed, disclosed or used without the express written consent of Abbott.

2. CardioMEMS PA pressure data during collection of right heart catheterization (RHC) data, when done as standard of care, will be summarized over 6 months.
3. LVAD speed, power, and estimated flow parameters will be summarized over 6 months.
4. Heart Failure medications will be summarized as both counts and total daily dosage according to class of medication at baseline 1, 3, and 6 months.

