Appendix F: Management of Hemodynamic Parameters

The CardioMEMS HF System allows intermittent assessment of pulmonary artery systolic, diastolic and mean pulmonary artery pressures. Hemodynamic information obtained by the system should be used for clinical decision making in addition to symptoms, weights or physical examination (traditional markers of volume).

Target Pulmonary Artery Diastolic Pressure Range: 8 - 15 mmHg

Initially, thresholds will be set automatically at the CardioMEMS commercially acceptable range. The physician will then adjust the thresholds to the specified range above, specifically for each patient. These threshold notifications are intended to guide the physician to review the Merlin.net website. Every attempt should be made to keep the pulmonary artery pressures within the specified pulmonary artery pressure ranges utilizing the guidelines. In order to clinically manage patient's PA pressures, the physician must review the PA pressure measurements on a frequent basis, for example, some patients may require a daily review of their PA pressure measurements, while some patients may need a weekly review. The physician or designee has unlimited access to the Merlin.net website.

An elevation of pressures beyond the patient's pressure ranges should be considered a volume overloaded status and should be managed using one of the recommended treatment options listed below.

A decrease in the pulmonary pressures below the patient's pressure ranges should be considered a volume depletion event and managed using one of the recommended treatment options listed below.

Diuretics and vasodilators should be adjusted based on the patient's baseline diuretic requirement, knowledge of the patient's prior response to these agents, and clinician judgment to accomplish the pressure goals set forth in this guideline.

The PA pressure readings should be used in addition to weights, signs and symptoms, laboratory values and other traditional markers of volume in the management of heart failure. It is important to review the trend of PA pressures. As with all other diagnostic information, physicians should consider the entire medical history of each patient when initiating or modifying therapies.

Recommended Treatment Options:

- Diuretic Management
- Vasodilators such as nitrates and hydralazine
- Titration of HF medications
- LVAD Speed Changes

Table 6 – Recommended Frequency of CardioMEMS HF System Review

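### Endpoint 3 is given the job of showing what medication and pump-speed changes do to PA pressure, but it is tied to no logged change and counts days above and below range alike

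*Combined protocol and SAP*

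**What the plan says.** Section 4.2 lists three objectives. The third has two halves: to evaluate PA pressure target ranges, and to "assess the impact of medication and pump speed changes on PA pressures". The second half is at issue here.

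The analysis text gives that half to a single measure. In Section 6, under the third objective, the relevant sentence begins "The percentage of days that PA pressure is in the target range at different points in the study will be used to assess". Its object is the effect of medication and speed changes. Section 6.1.1 item 3 defines the measure as days with PA diastolic pressure in 8-15 mmHg divided by days with a measurement, over 6 months and at further points that are not named. It then repeats the purpose: "This endpoint will be used to assess the impact of medication and pump speed changes on PA pressures".

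The surrounding text matters in three ways.

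- **Direction.** Appendix F says that pressure above range "should be considered a volume overloaded status" and that pressure below range "should be considered a volume depletion event".
- **Logs.** Sections 4.1, 5.6 and 5.8.1 and the note to Table 2 require medication and pump-speed changes to be recorded, with reasons. Section 4.1 also requires a rationale when pressure is out of range and nothing is changed.
- **Other analyses.** Endpoint 2 summarises PA pressures over time, and Section 6 adds raw pressures at 1, 3 and 6 months. Section 5.9 collects PA readings "with each change in pump speed" during ramp tests, which Section 6.1.2 item 1 summarises when they are done as standard of care. Section 6.1.2 also states "LVAD speed, power, and estimated flow parameters will be summarized over 6 months" and "Heart Failure medications will be summarized as both counts and total daily dosage according to class of medication", the latter at baseline and months 1, 3 and 6.

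**The concern.** To describe the impact of a change, a summary needs to know when the change happened and which way pressure moved afterwards. Endpoint 3 as written has neither. Its time points are not tied to changes, and a day at 20 mmHg counts the same as a day at 5 mmHg. A treatment response that carried a patient from overload through the range into depletion could leave the percentage where it started.

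What is at stake is half of one of the three listed objectives. The study is meant to inform treatment strategies and later trials (Sections 2 and 4.2). Section 4.1 recommends diuretic adjustment as the first approach and expects speed changes to be infrequent. The most frequent kind of change is therefore the one that ramp tests say nothing about. The target-range half of the objective is not affected.

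**Working it through.** The plan gives no figure to reproduce. The sample size of 100 has no stated SD or effect size, and the documents give no variability for PA diastolic pressure. The finding rests on the definition. The numbers below show its consequences under stated assumptions.

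**1. Direction is lost.** Input from the plan: range 8-15 mmHg. Assumed: daily pressure normal with mean m and within-patient SD s of 2-5 mmHg. The share in range is Φ((15−m)/s) − Φ((8−m)/s).

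| s | in range, m = 17 | in range, m = 6 | above 15 if m = 17 (= below 8 if m = 6) |
|---|---|---|---|
| 2 | 15.9% | 15.9% | 84.1% |
| 3 | 25.1% | 25.1% | 74.8% |
| 4 | 29.6% | 29.6% | 69.1% |
| 5 | 30.9% | 30.9% | 65.5% |

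The match is exact because 17 and 6 lie equally far from the midpoint, 11.5. A three-way split separates the two patients at once.

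**2. Sensitivity depends on the starting point.** Same formula, same 3 mmHg fall:

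- From 22 to 19 mmHg: 0.0% to 2.3% (s = 2, +2.3 points); 7.8% to 19.8% (s = 5, +12.0 points).
- From 17 to 14 mmHg: 15.9% to 69.0% (s = 2, +53.1 points); 30.9% to 46.4% (s = 5, +15.6 points).

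**3. A before/after summary has its own bias.** Changes are prompted by out-of-range readings, so pressure would tend to drift back even with no effect. To size this, take X as the mean of days −7 to −1 and Y as the mean of days 8 to 14. Assumed: AR(1) daily pressures with ρ 0.5-0.9, within-patient SD 2-5, between-patient SD B of 3 or 4, cohort mean μ and zero treatment effect. Let r0 be the mean of ρ^|i−j| over pairs of days within a window, and r1 the mean across the two windows. Then:

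- V = B² + s²·r0 and C = B² + s²·r1.
- Expected change given X > 15 = (C/V − 1)·√V·φ(z)/(1 − Φ(z)), with z = (15 − μ)/√V.
- Given X < 8 = (1 − C/V)·√V·φ(z)/Φ(z), with z = (8 − μ)/√V.

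Worked case: μ = 10, s = 5, B = 3, ρ = 0.8. Here r0 = 0.641 and r1 = 0.043, so V = 25.0, C = 10.1 and C/V − 1 = −0.597. With z = 1.00, the tail term is 5.00 × 1.525 = 7.63, and the expected change is −4.6 mmHg.

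| μ (assumed) | fall after weeks above 15 | rise after weeks below 8 |
|---|---|---|
| 15 | 0.3-2.4 mmHg | 0.7-5.5 mmHg |
| 10-22 | 0.02-4.6 mmHg | 0.4-9.3 mmHg |

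The documents give no cohort mean, so the wider row is the one to use.

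**4. Precision when episodes are few.** With the same windows and seven readings in each, the SD of one signed change, s·√(2·r0 − 2·r1), runs from 1.67 to 5.56 mmHg. If 10 patients had one speed change each (assumed), the 95% half-width is t(0.975, 9)·SD/√10 = 1.2 to 4.0 mmHg, before any true variation in response.

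**5. Comparison within the plan.** For the six-minute walk, Section 6.1.1 item 4 specifies a signed change in pressure from before to after the event, at named visits. Nothing comparable is specified for medication or speed changes.

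**The case against.** The strongest reply is that the study is not as bare as endpoint 3 alone suggests. Endpoint 2 and the raw pressures at months 1, 3 and 6 keep direction. Medication counts and daily doses are tabulated at those same visits, so a reader can set pressure beside treatment intensity for the cohort. Ramp tests pair speed steps with readings. The study is a descriptive feasibility study with no success criteria (Section 6.4), and a before/after summary would be confounded.

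Most of this stands, and it limits the point. Loss of direction in endpoint 3 can largely be made good at cohort level. Cohort tables side by side do not, however, show what happened in the patients whose treatment changed, or when. Ramp tests occur only when done as standard of care, and they do not bear on drugs. The descriptive purpose is no defence either, since the proposed repair is also descriptive.

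A reader might go further and infer that the report will contain nothing on pressure after a medication change. The documents do not support that. The unnamed points are not barred from falling around logged changes, and nothing forbids a linked analysis. What can be said is that the plan does not commit to one.

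**Conclusion.** The concern holds, limited to the use assigned to endpoint 3. The percentage in range, as defined, cannot by itself assess the impact of medication and pump-speed changes, and no other planned analysis joins the change logs to PA pressure within patients. The plan is underspecified here. It does not exclude the analysis, and it does not leave the direction of pressure unreported.

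The textual finding needs no assumptions. Its size does: normal daily pressures with within-patient SD 2-5 mmHg. On those, opposite states share a score of 16-31%, and an identical 3 mmHg fall registers as anything from 2 to 53 points. The regression-to-the-mean figures also depend on an unknown cohort mean and an assumed autocorrelation. They show that caution is needed and do not predict the trial's result. This should be fixed, but it does not threaten the study as a whole.

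**What to change.** In Section 6 (third objective) and Section 6.1.1 item 3:

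1. Report the percentage of measured days below 8, within 8-15 and above 15 mmHg separately, at named time points, for example months 1, 3 and 6.
2. Add a descriptive within-patient summary of the signed change in mean PA diastolic pressure between pre-specified windows before and after each logged change, by type and direction of change. The sponsor sets the windows; those used in the working are only an example. State a minimum number of readings per window, flag episodes with a further change inside the window, and show documented out-of-range episodes without a change alongside, where they can be dated. Describe the result as association only. Regression to the mean is expected, and the no-change episodes are chosen on clinical grounds.
3. If step 2 is not adopted, delete the statements in both sections that this percentage will be used to assess the impact of the changes.

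The cost is SAP wording and modest programming, with no new visits or procedures. Home readings follow standard of care (Section 5.8.5), so some windows will be sparse or empty, and the number of unusable episodes should be reported. Speed-change cells will be thin and may have to be listed instead of summarised. The documents name no date field for logged changes and no log for no-change episodes. The sponsor should confirm that both exist in usable form; if they do not, some CRF work would be needed.
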